## 1. Introduction

This document is a comprehensive data collecting tool which was created to assist all types of researchers. It consists of general guidelines for measuring anthropometric and physiological factors, and blood sampling with reference to the methods mentioned in the literature and the manuals of the equipment.

This document describes the standard operating procedure (**SOP**) for the measurements of anthropometric and physiological factors that include weight, body composition, height, peak power output, heart rate,  $VO_2$  MAX, and exhaustion time, and the SOP for blood sampling.

Furthermore, it indicates the **SOP** for measuring plasma hemoglobin and hematocrit, creatine kinase (**CK**) levels, and the cytokines of proinflammatory **IL-6**, and **TNF- $\alpha$** , and the anti-inflammatory **IL-10**. CK to be measured using an autoanalyzer (**Cobas C111**), IL-6 (**Cobas C411**), while TNF- $\alpha$  and IL-10 with ELISA.

The research assistance team are fully responsible for following the guidelines which should be governed by the ethics code.

## 2. General guidelines

Before starting the experiment, you need to be familiar with the tasks you are planning to do, the equipment you are responsible for, and the machines you are going to use. Below are some of the main guidelines:

- Use the equipment according to its manual.
- Clean the tools and equipment after each use.
- Sample labeling, handling and storage conditions are crucial and affect the success of your experiment.
- Create an identification code for each participant for confidentiality purposes.
- Measurements and data recordings must be taken in a pair.
- Follow safety rules in the laboratory.

## Anthropometric Measurements

### - Height measurement guidelines

You will measure the weight of the participants using digital column scale (**Seca GmbH**) according to the following steps:

1. Calibrate the scale and place it on a flat surface.
2. Instruct the participant to take off shoes and any hair attachments and stand straight against the backboard of the scale with shoulder and head touching the wall.
3. Participants' heels should be close to each other.
4. Record the measurement once displayed.

### - Guidelines for measuring weight and body composition

Weight and body composition will be measured using the same device (**InBody 720, Precise Body Composition Analyzer**). Below are the steps to be followed:

1. Advise all participants to:
  - Refrain from food or drinks 3 hours before taking the measurement.
  - Wear light clothes.
  - Empty bladder at least 30 minutes prior to testing.
2. Ask the participant to take off shoes and to get rid of any heavy item that would affect the reading.
3. Participant should stand barefoot on the metal foot electrodes with holding the hand electrodes firmly and straight down.
4. Instruct the participant to keep calm with no movement until you take the reading.
5. Test repeats should be taken at the same time of the day under similar conditions.

**Figure 1** InBody 720 body composition analyzer  
(1)

### - Determination of peak power output

With the help of a cycle-Ergometer, we can check the determine both peak power output (PPO).

#### Cycle-Ergometer guidelines

1. It is a machine with a manual you need to follow to finish the setup.
2. Ensure the participant wears proper exercise clothing.
3. Connect all sensors and place them on the participant's body.

4. Under full supervision, instruct the participants to warm up their muscles at low intensity.
5. Start increasing the resistance following the predetermined protocol.

### **Peak power output (PPO)**

When the participant is no longer able to continue pedaling, a cool down at low intensity should be followed, and the PPO is the highest level of power in (watts) is recorded.

#### **- Measuring Heart rate guidelines **

1. Connect the Polar H10 heart rate sensor before the start of the intended physical activity.
2. Place it below the chest muscle, and don't make it too tight nor too loose.
3. The electrodes should be moistened with conductive gel or water.
4. Pair it with a compatible device (mobile, tablet or any fitness equipment) using Bluetooth.
5. After the finish of the activity, wait a few minutes to ensure the device records the heart rate during the recovery period.
6. Disconnect the strap and rinse it with water if necessary.

#### **- The guidelines for the assessment of the maximal oxygen consumption ( $VO_{2\text{ MAX}}$ ) **

1. Place the necessary sensors and electrodes on the participant, which may include a face and a pulse oximeter for monitoring oxygen saturation prior to the start of the training.
2. Calibrate the metabolic cart to room temperature (21 – 23 °C) and to gases of the concentration (16.00%  $O_2$  and 3.99%  $CO_2$ )
3.  $VO_2$  is recorded every 15 seconds during the exercise as, and when it reaches a plateau, the  $VO_{2\text{ MAX}}$  is achieved.
4.  $VO_{2\text{ MAX}}$  is expressed in mL of oxygen / kg of body weight (mL/Kg/min).

## **Blood Sampling**

### **- Taking blood sample**

It is necessary to follow strict guidelines when taking a blood sample from the participant/patient, and it should be done by a licensed technician. Below are the steps:

1. Prepare all the supplies to be used.

2. Wash your hands and wear clean gloves.
3. Apply a tourniquet a few centimeters above the puncture site and identify a suitable vein.
4. With alcohol swab, clean the area and allow it to dry.
5. Insert the needle into the vein smoothly and connect it to an anticoagulant tube to allow the blood to flow into it.
6. Disconnect the tube, and then remove the needle.
7. Apply a cotton ball to the puncture site to stop the bleeding, and then apply a bandage over the puncture site.
8. Discard the needle in a designated medical waste container.
9. Label the tube properly.
10. Invert the tube gently to mix the blood.
11. Store it at (4 – 8) °C for a maximum of 24 hours.

[figure not shown]

Figure 2 Steps for taking blood sample (4)

#### - Collecting blood plasma

From the blood sample collected from the participants, plasma can be collected as follows:

1. Centrifuge the blood sample at (3200 to 3500) rpm for 10 to 15 minutes.
2. Transfer the top plasma layer to another tube.
3. Store at -80 °C for further analysis.

## Hemoglobin and Hematocrit measurement

The laboratory device **HemoCue** is to be used to measure both hemoglobin and hematocrit levels in the blood. Below are the steps (5):

1. The cuvette holder of the device should be in the loading position.
2. Ensure the participant's hand is warm and relaxed.
3. Clean the participant's ring or middle finger with disinfectant and let it dry.
4. Stimulate blood flow by applying a light pressure from the top of the knuckle toward the fingertip.

5. Use a lancet to prick the finger.
6. Wipe away the first (1-3) blood drops.
7. Press again lightly until another drop appears and transfer it onto the microcuvette of the HemoCue.
8. Wipe off any excess blood from the edges of the microcuvette.
9. Insert it into the HemoCue device.
10. Push the holder to its measuring position.
11. The hemoglobin and /or hematocrit concentration is displayed on screen.
12. Discard the microcuvette after measurement.

## Creatine kinase (CK) assay

CK can be quantitatively determined from blood plasma sample using cobas c111 bench-top analyzer from Roche Diagnostics.

### - Guidelines for using c111 analyzer to measure CK 

1. Switch on the machine.
2. Log on the system
3. Check the internal fluids including wash bottle that is filled with distilled water, in addition to the liquid and the solid waste containers.
4. Load the reagents from the CK kit, and the other materials required for the test in the reagent disk in the analyzer.
- Kit reagents are: R1(Imidazole buffer) and SR (CAPSO buffer)
- The other materials: Calibrator f.a.s., Precinorm U plus, Precipath U plus, Preci Control Clin Chem Multi 1, Preci Control Clin Chem Multi 2, and NaCl Diluent 9 %.
5. Prepare the system from the screen.
  - a. Perform a maintenance action.
  - b. Scan the reagents.
  - c. Check the cuvettes.
  - d. Perform mixing.
  - e. Identify the sample.
6. Perform calibrations.

7. Perform quality control, if pass, you can start the test.
8. Identify the sample.
9. Select the tests.
10. Place your sample tubes (up to 8 samples per run)
11. Start the run.
12. The cobas c 111 analyzer automatically calculates the analyte activity of each sample.

Conversion factor:  $U/L \times 0.0167 = \mu\text{kat/L}$

## Cytokines measurement

The proinflammatory cytokines Interleukin-6 (IL-6) can be determined using Cobas analyzer e411, while the pro-inflammatory cytokine Tumor Necrosis Factor alpha (TNF- $\alpha$ ) and the anti-inflammatory cytokines Interleukin-10 (IL-10) can be determined with ELISA.

### - Guidelines for using cobas analyzer e411 to measure IL-6 (7)

1. Prepare the machine.
  - a. Make sure the surfaces of the analyzer and the probes are clean and undamaged.
  - b. Check the pinch valve tubing.
  - c. Ensure the pipetter syringes and tubing have no bubbles.
  - d. Fill the wash bottle with distilled water and SysWash.
  - e. Empty the liquid waste bottle and waste box. (if necessary)
2. Switch on the machine
3. Bring the cooled reagents to 20 °C and place them in the reagent disk of the analyzer (its temperature 20 °C)
4. From the screen, start a calibration. Calibration must be performed once per reagent lot using fresh reagent.
5. Perform a quality control check.
6. Centrifuge the sample tubes (if necessary) and then place them in the analyzer (up to 30 samples/run), and note that samples should be cooled to 20 °C.
7. Program the samples and select the test.
8. Run the test.
9. Remove samples from the analyzer after the test finishes.

10. After the test finishes, the analyzer automatically calculates the analyte concentration of each sample in pg/mL (picograms per milliliter).

- **Guidelines for ELISA (8)**

1. Prepare all reagents, samples and standards as instructed in the kit.
2. Add 50  $\mu$ L of your sample or standard to appropriate wells.
3. Add 50  $\mu$ L of the antibody cocktail to each well.
4. Seal and incubate for 1 hour at room temperature on plate shaker set 400 rpm.
5. Aspirate and wash each well with 3 x 350  $\mu$ L 1x wash buffer for at least 10 seconds.
6. After the last wash, invert the plate on a clean paper towel.
7. Add 100  $\mu$ L of TMB development solution and incubate for 10 minutes at 400 rpm plate shaker.
8. Add 100  $\mu$ L stop solution to each well followed by 1 min shake.
9. Record at 450 nm.

# 1- Changes history

All changes and versions of this document are reported in the table below:

| Version | Author              | Description of modifications | Date       |
|---------|---------------------|------------------------------|------------|
| V1      | [name] | First version                | 12/08/2024 |
|         |                     |                              |            |
|         |                     |                              |            |
|         |                     |                              |            |
|         |                     |                              |            |
|         |                     |                              |            |
|         |                     |                              |            |

---

## 2 - Definitions

CM Camel Milk

## 3 - Objectives

### 3.1 Primary Endpoint

- To assess the impact of camel milk on exercise recovery and subsequent physical performance

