### 3.2 Secondary Endpoints

- Check impact on inflammatory markers.

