#### 4.4 Sample size calculation

Sample size was calculated with the use of G\*Power 3. 1.9.7 that revealed the need for 12 participants to achieve a 0.95 power of the test with medium effect size and alpha set at a 0.05 value. Thus, a minimum of 12 participants will be recruited for the current study.

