## 5 - Measured variables retained for the analysis

**Table of variables**

| Variables             | Format  | Description                      |
|-----------------------|---------|----------------------------------|
| Code                  | String  | Three letter code of participant |
| Date                  | Date    | Date of data collection          |
| Time                  | Numeric | Time of data collection          |
| Sex                   | Numeric | Sex: male or female              |
| Age                   | Numeric | Age in years                     |
| Marital               | Numeric | Marital status                   |
| Education             | Numeric | Education level                  |
| Self-Health           | Numeric | Self-perceived health            |
| Wt                    | Numeric | Self-reported weight in kg       |
| Ht                    | Numeric | Self-reported height in cm       |
| Order                 | Numeric | Random order of trial            |
| Visit                 | Numeric |                                  |
| Treatment_Drink       | Numeric |                                  |
| Treatment_Recognition | Numeric |                                  |
| Session               | Numeric |                                  |
| BMI_Measured          | Numeric |                                  |
| HR_rest               | Numeric |                                  |
| HR_Peak               | Numeric |                                  |
| RPE_rest              | Numeric |                                  |

|           |         |  |
|-----------|---------|--|
| RPE_Peak  | Numeric |  |
| VO2 rest  | Numeric |  |
| VO2 Peak  | Numeric |  |
| RQ rest   | Numeric |  |
| RQ Peak   | Numeric |  |
| Cytokine1 | Numeric |  |
| Cytokine2 | Numeric |  |
| Cytokine3 | Numeric |  |
| CK        | Numeric |  |

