### 6.2 Methods of Analysis

#### 6.2.1 Principal Analysis

The Chi-square test will be used to assess the impact of demographics on dependent variables. The repeated measures ANOVA will be used to assess main effects. One way ANOVA and t-test will be used to compare effects of independent variables on measured variables. A p value  $<0.05$  will be considered statistically significant. Effect size will be calculated and presented to provide an estimation of the significance magnitude. If appropriate the 95% confidence interval will be reported.

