#### 6.2.2 Secondary Analysis

The same methods will be used to assess the impact inflammation markers.

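### The SAP names no primary variable or contrast and tests up to nine candidate outcomes at 0.05 without multiplicity control, so the error rate for its primary aim is well above 5%

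*SAP*

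**What the plan says.** - **Primary endpoint (SAP 3.1).** The whole entry is "To assess the impact of camel milk on exercise recovery and subsequent physical performance". It covers two constructs, recovery and performance, and gives no variable, time point, comparator or contrast.
- **Secondary endpoint (SAP 3.2).** "Check impact on inflammatory markers".
- **Candidate outcomes (SAP 5, "Measured variables retained for the analysis").** The table lists heart rate, RPE, VO2 and RQ, each at rest and at peak, plus CK and three cytokines. Their description cells are blank, and nothing is labelled primary, recovery or performance.
- **Testing (SAP 6.2.1).** Repeated measures ANOVA is for main effects. In addition, "One way ANOVA and t-test will be used to compare effects of independent variables on measured variables". A p value below 0.05 "will be considered statistically significant". The section does not list the variables or state sidedness.
- **Cytokines (SAP 6.2.2).** "The same methods will be used to assess the impact inflammation markers".
- **Sample size (SAP 4.4).** The calculation gives "the need for 12 participants to achieve a 0.95 power of the test", with "medium effect size and alpha set at a 0.05 value". It does not say which variable or test this is for.

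The protocol is a measurement procedure manual and ranks no endpoints. Its Introduction lists peak power output and exhaustion time among the measurements. Neither is in the SAP variable table.

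**The concern.** A 5% threshold limits false conclusions to 5% only when one prespecified test decides the question. Here the aim is broad and several variables could be read as bearing on it. The choice of which variable represents recovery or performance could therefore be made after the results are seen. A significant result on any one of them could be presented as meeting the primary aim, and nothing in the SAP would count against it. What is at stake is whether a positive finding from this trial can be taken at its nominal error rate.

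**Working it through.** **1. The plan's own figure.** The documents give no family-wise error rate. The only design figure is N = 12 for power 0.95, a medium effect and alpha 0.05. Taking medium as dz = 0.5 or f = 0.25 (conventional values, an assumption):

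- Paired t-test: N = 54 two-sided or 45 one-sided. Power at N = 12 is 35% or 49%.
- Repeated measures ANOVA, within-person correlation 0.5: N = 54 with 2 measurements, 43 with 3.
- N = 12 is reached with other inputs, for example correlation 0.8 with 6 measurements, or 0.75 with 8.

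The SAP states neither the correlation nor the number of measurements, so 12 can be neither confirmed nor refuted. The figure does not reveal an implied primary variable.

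**2. Inputs for the error rate.**

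- Non-cytokine candidates (SAP 5): 4 measures × 2 (rest, peak) + CK = 9.
- Cytokines, declared secondary (SAP 3.2): 3.
- Per-test level (SAP 6.2.1): 0.05, taken as two-sided, so 0.025 in the benefit direction. This assumes that each variable has one favourable direction.
- One camel milk contrast per variable (assumption).

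**3. Independent tests.** Chance of at least one false positive among k tests:

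- Either direction: 1 − 0.95^k
- Benefit direction: 1 − 0.975^k

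| k | Either direction | Benefit direction |
|---|---|---|
| 1 (one prespecified test) | 5% | 2.5% |
| 5 (four peak values and CK) | 1 − 0.95^5 = 23% | 1 − 0.975^5 = 12% |
| 9 (all non-cytokine) | 1 − 0.95^9 = 37% | 1 − 0.975^9 = 20% |
| 12 (cytokines added) | 1 − 0.95^12 = 46% | 1 − 0.975^12 = 26% |

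**4. Correlated outcomes.** Simulated paired t-tests, n = 12, nine variables with a common correlation, 20,000 replicates:

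| Correlation | Either direction | Benefit direction |
|---|---|---|
| 0 | 37% | 20% |
| 0.3 | 33% | 17% |
| 0.5 | 28% | 14% |
| 0.7 | 21% | 10% |
| 0.9 | 13% | 7% |

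**5. More contrasts (assumption).** Suppose there were three drinks and camel milk were compared with each of the other two without correction. The benefit-direction rate for nine variables would then be 34% at correlation 0 and 24% at 0.5 (10,000 replicates). The documents do not give the number of drinks. The three visits in the section 8.1 table shell do not establish it.

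**6. When a false positive becomes more likely than not.** For independent tests, the either-direction rate first passes 50% at 14 tests (1 − 0.95^14 = 51%). The benefit-direction rate first passes 50% at 28.

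**The case against.** A reader might infer that a false claim of benefit is likely. The documents do not support that. The 37% counts false positives in both directions and is below one half. The benefit-direction figure is 20%, and less with correlation, which is plausible because four measures appear as rest and peak pairs. Rates above 50% need further contrasts, sessions or tests, which the SAP leaves open but does not plan.

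A reader might also apply the 46% for all twelve variables to the primary aim. That does not hold either: sections 3.2 and 6.2.2 put the inflammatory markers in a separate secondary objective, so a significant cytokine would not meet the primary one.

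It is also fair to say that nine is an upper count. The SAP classifies none of the nine as a recovery or performance variable. The section 8.1 shell lists resting heart rate among the demographic characteristics, although with a p-value column. If all four resting values are descriptive, five variables remain and the figures are 23% and 12%. That each listed variable will be tested is itself a reading of section 6.2.1, which refers to the measured variables in general.

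Finally, section 6 speaks of a descriptive principle, and section 6.2.1 asks for effect sizes and, where appropriate, 95% intervals. The plan therefore leans partly towards estimation. It still sets a significance threshold for its principal analysis and claims 0.95 power, so the descriptive wording does not remove the problem.

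None of this supplies a primary variable or a multiplicity rule.

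**Conclusion.** The point holds in this form: no primary variable, time point or contrast is named, and the candidate outcomes are tested at 0.05 with no hierarchy or adjustment. That much is certain from the text.

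The size is conditional. If any of nine variables can satisfy the primary aim, with one contrast each, the either-direction rate is at most about 37% and the benefit-direction rate at most about 20%. A correlation of 0.5 gives about 28% and 14%. Five variables instead of nine give about 23% and 12% if independent. Several drink contrasts or sessions would raise these figures. Even at a correlation of 0.9 the nine-variable rate is about 13%, or 2.6 times the nominal 5% (13/5). The SAP should be corrected before the data are analysed.

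**What to change.** 1. In SAP 3.1, name one primary variable, one time point and one camel-milk-versus-comparator contrast, tested at two-sided 0.05. That restores 5% overall and 2.5% in the benefit direction. The comparator and the exercise bout at which the outcome is read must also be defined, since neither document does so.
2. If peak power output or exhaustion time is chosen, add it to the section 5 table. For exhaustion time, the protocol also needs a measurement procedure, because it describes none.
3. Tie the section 4.4 sample size to the chosen variable and test, and state the effect size, correlation and number of measurements used.
4. Treat the other variables as secondary. Either apply Holm to the remaining non-cytokine variables and separately to the three cytokines, or report estimates with 95% intervals and no significance claim.

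**Cost.** The non-primary variables face a stricter threshold or carry no significance claim. Under Holm the smallest p value must meet 0.05/9 = 0.0056 if nine non-cytokine variables remain, 0.05/8 = 0.0063 if eight remain, and 0.05/3 = 0.017 for the cytokines. The SAP needs small additions to its variable table and definitions. If the restated sample size calculation does not support 12, recruitment would have to be reconsidered.

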### 3.2 Secondary Endpoints

- Check impact on inflammatory markers.

## 4 - Project Design

The study will use randomized crossover counterbalanced design to collect information about impact of camel milk on physical performance.

### 4.1 Inclusion criteria

The inclusion criteria for this study are the following:

- (1) Recreational athlete, active 5 days a week.
- (2) Male, healthy, non-obese.
- (3) Age 18 to 39 years old.
- (4) No allergies to milk.
- (4) provide consent to participate and able and ready to complete the study's interview.
- (5) Speaking and understanding Arabic or English, and open to visit him at home.
- (6) Subject consenting to participate in the study.

#### 4.2 Exclusion criteria

- (1) Sedentary
- (2) Female
- (3) Allergies to milk
- (4) Presence of diseases.

#### 4.3 Sampling

The sample for this study will be obtained from UAEU community populations.

#### 4.4 Sample size calculation

Sample size was calculated with the use of G\*Power 3. 1.9.7 that revealed the need for 12 participants to achieve a 0.95 power of the test with medium effect size and alpha set at a 0.05 value. Thus, a minimum of 12 participants will be recruited for the current study.

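### The claim of 0.95 power for a medium effect with 12 participants is not supported by the inputs the SAP gives; with two or three conditions and a correlation of 0.5, power is about 0.35 to 0.41

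*SAP*

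**What the plan says.** SAP section 4.4 says that G*Power 3.1.9.7 showed "the need for 12 participants to achieve a 0.95 power of the test with medium effect size and alpha set at a 0.05 value", and concludes that "a minimum of 12 participants will be recruited for the current study". It gives no dropout allowance.

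On design, SAP section 4 says "The study will use randomized crossover counterbalanced design", without the number of drinks or periods. On analysis, SAP section 6.2.1 says "The repeated measures ANOVA will be used to assess main effects", and also names one-way ANOVA and t-tests. Neither section says which test the sample size was computed for.

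The variable table in SAP section 5 lists a visit, a treatment drink and a session, without levels. The demographic table shell in section 8.1 has columns for three visits. The Protocol is a measurement procedure manual and says nothing on sample size.

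**The concern.** In a crossover, the sample size for a given effect depends strongly on how many measurements each participant contributes and how highly they correlate. The SAP gives neither. At conventional values for a within-participant comparison, 12 participants fall far short of 0.95 power for a medium effect.

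A stated power of 0.95 tells readers how to take a non-significant result. If it were true, such a result would be fair evidence against a medium effect of camel milk. If the true figure is nearer 0.4, a non-significant result says little about a medium effect.

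**Working it through.** **Inputs from SAP section 4.4:** N = 12, target power 0.95, alpha 0.05, and an effect called medium.

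**Assumptions, because the SAP is silent:** medium means f = 0.25 for ANOVA or dz = 0.5 for a paired t-test. The number of repeated measurements m is 2 or 3, with larger values also tried. The correlation rho is 0.5, then varied. Sphericity holds, and the t-test is two-sided.

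**Formulas.** For the within-participant main effect in a repeated-measures ANOVA, the noncentrality is lambda = f² × N × m / (1 − rho), with df1 = m − 1 and df2 = (N − 1)(m − 1). Power is the probability that a noncentral F with these parameters exceeds the 5% critical value. For the paired t-test the noncentrality is dz × √N on N − 1 degrees of freedom.

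**Step 1: try to reproduce 12 at f = 0.25 and rho = 0.5.**
- Two conditions: lambda = 0.0625 × 12 × 2 / 0.5 = 3.0 on 1 and 11 df; power 0.353.
- Three conditions: lambda = 0.0625 × 12 × 3 / 0.5 = 4.5 on 2 and 22 df; power 0.409.
- Paired t, dz = 0.5: noncentrality 0.5 × √12 = 1.73; power 0.353, the same as the two-condition ANOVA. A one-sided test gives 0.492 and needs 45 participants.

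**Step 2: find what would make 12 sufficient.** All rows use N = 12, except the column for required N.

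| Measurements (m) | Power at f = 0.25, rho = 0.5 | N for 0.95 at f = 0.25, rho = 0.5 | Power at f = 0.25, rho = 0.8 | rho giving 0.95 at f = 0.25 | f giving 0.95 at rho = 0.5 |
|---|---|---|---|---|---|
| 2 | 0.353 | 54 | 0.704 | 0.905 | 0.573 |
| 3 | 0.409 | 43 | 0.806 | 0.874 | 0.497 |
| 4 | 0.467 | 36 | 0.879 | 0.845 | 0.449 |
| 6 | 0.574 | 28 | 0.956 | 0.794 | 0.390 |

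At rho = 0.5, adding measurements alone is a slow route: power is still 0.795 with 12 measurements and first passes 0.95 at 23.

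The SAP's 12 is therefore the exact requirement under several input sets. With f = 0.50, m = 3 and rho = 0.5, power is 0.952 at N = 12 and 0.930 at N = 11. With f = 0.25 kept, power at N = 12 is 0.956 for m = 4 and rho = 0.85, 0.956 for m = 6 and rho = 0.80, and 0.951 for m = 8 and rho = 0.75.

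**Step 3: effect detectable with 12 at 95% power and rho = 0.5.** With two conditions, f is about 0.57. At this correlation dz = 2f, so dz = 2 × 0.573 ≈ 1.15. With three conditions, f is about 0.50. No single dz corresponds to that figure, because the pairwise differences depend on the pattern of the means.

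**Step 4: sensitivity.** With three conditions, departures from sphericity lower the 0.409 to 0.346 (epsilon 0.75) or 0.278 (epsilon 0.5).

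**The case against.** The strongest reply is that a calculation with unstated inputs cannot be shown to be wrong. G*Power lets the user set both the number of measurements and the correlation, and Step 2 shows that 12 is exactly right for f = 0.25 under several settings. The SAP also lists sessions as well as visits, so the within-participant factor may have more than three levels. This stands. The defect shown is an unsupported claim, not a proven slip in arithmetic.

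It limits three inferences that a reader might draw:
- That 12 can come only from an effect twice medium. A high correlation, or more measurements with a raised correlation, gives the same number at f = 0.25.
- That a medium d of 0.5 was entered where the program expects f. The match at f = 0.50 is one of several, and the SAP gives no numeric effect size to check it against.
- That there are three drinks. The three columns in section 8.1 are visits, and one could be a baseline visit.

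The objection does not rescue the claim. With two or three conditions even a correlation of 0.8 leaves power at 0.70 or 0.81. The paired t-test with dz = 0.5 gives 0.353 whatever the correlation, because dz already contains it. Nor is a main effect across many sessions the drink comparison that the primary objective calls for.

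No section says that a non-significant result will be read as no effect. Sections 6 and 6.2.1 plan effect sizes and, where appropriate, 95% confidence intervals, which would show some of the imprecision. That reduces the harm but leaves the power statement uncorrected.

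**Conclusion.** The statement of 0.95 power for a medium effect with 12 participants is not supported by the inputs given. At f = 0.25, correlation 0.5 and sphericity, power is about 0.35 (two conditions) or 0.41 (three), against required sizes of 54 or 43.

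These powers are conditional on assumed inputs. A reader might take 0.35 to 0.41 as the trial's true power, but the documents do not fix the correlation or the number of conditions. Either an influential correlation assumption (about 0.905 for two conditions, 0.874 for three) or number of measurements has been left out, or the effect assumed is larger than f = 0.25. In each case section 4.4 needs correcting, because the trial relies on this figure. Any shortfall below 12 completers would lower power further.

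**What to change.** Keep the minimum of 12. In SAP section 4.4, state the test, the endpoint, the number of conditions, the numeric effect size with its metric, the assumed correlation, the sphericity assumption and any dropout allowance. Then restate the power for the drink comparison.

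If data support a correlation of about 0.905 (two conditions) or 0.874 (three) or more for the primary outcome, cite them, and the 0.95 can stay. Otherwise replace it with:
- the power obtained, for example 0.35 for two conditions or 0.41 for three at f = 0.25 and correlation 0.5;
- the effect detectable with 12 at 95% power and correlation 0.5: f about 0.57 for two conditions (paired dz about 1.15), or f about 0.50 for three;
- a sentence that a non-significant result does not exclude a medium effect.

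Use only the case that matches the actual number of conditions. The cost is SAP wording and a less favourable stated power; no extra participants are needed.
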